# 3.2. Sample Size and Power

As the PTI-125-10 study is primarily focused on long-term safety of simufilam from rollover studies PTI-125-06 and PTI-125-07, no formal sample size was calculated.

#### 3.3. Study Population

The study population is comprised of 1081 participants with mild-to-moderate AD. Participants are enrolled from approximately 141 clinical sites in the USA, Canada, the Republic of Korea, and Australia. For subjects electing to participate, the clinical and laboratory assessments from the Week 76 (PTI-125-06) or Week 52 (PTI-125-07) End-of-Treatment visit served as Baseline Visit assessments for the open-label study on Study Day 1.

#### 3.4. Treatments Administered

All participants received simufilam 100 mg tablets BID.

#### 3.5. Method of Assigning Subjects to Treatment Groups

This is an open-label, non-randomized study. All the participants received simufilam 100 mg tablets twice daily.

# 3.6. Blinding and Unblinding

All participants, investigators, and study personnel are aware of the treatment assignment and receipt of study drug during the conduct of the study, through database lock.

# 3.7. Schedule of Events

**Table 1: Schedule of Events** 

[figure not shown]
Procedures	Baseline Visit (Study Day 1)	Week 4	Week 16	Week 28	Week 40	Week 52 ET/ED 	Week 53 to 54
Informed Consent	X						
I/E Criteria	X						
Adverse Events	X	X	X	X	X	X	X
Concomitant Meds	X	X	X	X	X	X	
Vital signs	X	X	X	X	X	X	
Brief Physical Examination	X	X	X	X	X	X	
Brief Neurologic Examination	X	X	X	X	X	X	
Height	X						
Weight	X	X	X	X	X	X	
Resting ECG	X	X		X		X	
Biochemistry, Hematology, Urinalysis	X	X		X		X	
HbA1c 	X			X 		X 	
C-SSRS 	X	X	X	X	X	X	
Drug Dispensation	$X^2$	X	X	X	X		
Drug Accountability		X	X	X	X	X	
End of Study Follow- up Phone Call							X

- 1. On Study Day 1, as well as all remaining visits, the 'C-SSRS Since Last Visit' version will be administered.
- 2. The first dose of study drug is administered at the clinic to all subjects on Study Day 1 at least four hours after any prior dose and at least one hour before departure.
- 3. HbA1c collection will begin upon receipt of required supplies.
- 4. Week 28 and Week 52 HbA1c should only be collected in subjects with a Day 1 HbA1c.

# 4. Statistical Analysis and Reporting

# 4.1. Introduction

Data processing, tabulation of descriptive statistics, calculation of inferential statistics, and graphical representations will primarily use SAS (release 9.4 or higher). If the use of other software

is warranted, the final statistical methodology report will detail what software was used for what purposes.

Descriptive summaries of variables will be provided where appropriate. Continuous (quantitative) variable summaries will include the number of subjects (n) with non-missing values, mean, standard deviation (SD), median, minimum, and maximum.

Categorical (qualitative) variable summaries will include the frequency and percentage of subjects who are in the category for each value. In general, the denominator for the percentage calculation will be based upon the total number of subjects in the study population for the treatment group (or cohorts), unless otherwise specified.

The minimum and maximum will be reported with the same degree of precision (i.e., the same number of decimal places) as the observed data. Measures of location (mean and median) will be reported to 1 degree of precision more than the observed data and measures of spread (SD) will be reported to 2 degrees of precision more than the observed data.

Percentages will be presented to 1 decimal place, unless otherwise specified.

This study is considered an exploratory study. Statistical tests will be interpreted in an exploratory sense only and will not be considered formal hypothesis tests.

# 4.2. Interim Analysis and Data Monitoring

No interim analyses are planned.

An external DSMB will be involved in the management of this study. The DSMB meeting will be held periodically for the duration of the study. The purpose of the DSMB is to review the progress of the study with special regard to safety and make recommendations to the Sponsor on how to handle any safety concerns that arise. Further details regarding the DSMB can be found in the DSMB charter which was finalized before the first meeting was scheduled.

# 5. Analysis Populations

The following analysis populations are planned for this study:

[figure not shown]
• Safety Population (SAF): The SAF analysis set includes all participants who received at least one dose of study treatment. This population will be used for all safety analysis.

# 6. General Issues for Statistical Analysis

# **6.1.** Statistical Definitions and Algorithms

#### 6.1.1. Baseline

The last observation recorded before the first dose of treatment will be used as the baseline observation. The clinical and laboratory assessments performed at the Week 76 (PTI-125-06) or Week 52 (PTI-125-07) End-of-Treatment visit will serve as the baseline (Study Day 1) for this open-label extension study. In the event the End-of-Treatment visit and the Study Day 1 visit for the open-label extension study did not occur on the same date, the Medical Monitor was responsible for deciding whether any clinical and laboratory assessments needed to be repeated to

serve as baseline values for Study Day 1 depending upon the length of time between the two visits.

# **6.1.2.** Adjustments for Covariates

No covariates are planned for this study.

# **6.1.3.** Multiple Comparisons

No multiple comparisons are planned for this study.

#### 6.1.4. Handling of Dropouts or Missing Data

Although every attempt will be made to ensure participants remain in the study to completion and all data is collected as scheduled, the occurrence of missing data cannot be completely prevented.

An incomplete start or stop date of an AE will be imputed as described in section 6.1.8.

Any participant who withdraws from the study will be considered to have missing data at all subsequent visits.

# **6.1.5.** Pooling of Sites

No pooling of study centers is planned for this study.

# 6.1.6. Data Adjustments/Handling/Conventions

[figure not shown]
Only limited data required for analysis will be presented in listings or Clinical Data Interchange Standards Consortium (CDISC) datasets. Analysis results will be presented and summarized in either tables and/or listings. Data not subject to analysis according to this plan will not appear in any tables and listings.

The version 24.0 of the Medical Dictionary for Regulatory Activities (MedDRA) will be used to classify all AEs by system organ class (SOC) and preferred term (PT).

Ongoing AEs from the pivotal studies will be classified as TEAEs in the current study only if they increase in severity on or after the date of the first dose of study drug in the current study. Otherwise, they will be classified as medical history events.

Adverse events with entirely missing start dates will be classified as treatment-emergent, as appropriate.

For partial AE start dates: (a) if only the day is missing, and the month and year match the first dose date and the end date is on or after the first dose date, or AE is ongoing, then the date is assigned the first dose date thus the event will be considered as treatment-emergent; if the month and/or year do not match the first dose date or the end date is prior to the first dose date, then the day is assigned the first day of the month (01); (b) if month or the day and month are missing, and the year matches the first dose date and the end date is on or after the first dose date, or AE is ongoing, then the date is assigned the first dose date; if the year does not match the first dose date

or the end date is prior to the first dose date, then the day/month are assigned the first day of the year (01JAN).

For partial end dates: (a) if only the day is missing, then the day is assigned the last day of the month; (b) if both day and month are missing, they are assigned the last day of the year (31DEC).

Participants will be analyzed by the treatment received for all safety and tolerability assessments.

A treatment related AE is any AE with a relationship to the study drug of "Possibly Related" or "Probably Related" or "Reasonable Possibility".

If partial dates occur, the convention for replacing missing dates for the purpose of statistical analysis is as follows: if just day is missing then the day assigned is the first day of the month or the date of first dose (if in the same month), whichever is later; if just month is missing then the month assigned is the month of the first dose, unless that results in a date before the first dose in which case the month after the first dose is used; and if both month and day are missing then the month assigned is the month of the first dose and the day assigned is either the first day of the month or the first dose date, whichever is later.

If partial times occur, the convention is as follows: if the missing time occurs on the day of the first dose and both the hour and minute are missing then the time assigned is the time of the first dose, otherwise if both the hour and minute are missing and the date is not the date of first dose the time assigned is 12:00; if the date is the same as the date of the first dose and only hour is missing the hour assigned is 12 or the hour of first dose, whichever is later, and if the date is the same as the date of first dose and only the minute is missing the minute assigned is 30 or the minute of first dose, whichever is later. Otherwise, the hour assigned is 12 if the hour is missing and the date is not the same as the date of first dose and the minute assigned is 30 is the date is not the same as the date of first dose.

These conventions will be applied only to adverse event onset dates and times with the following precaution: if the missing date and time reflect the date and time of onset of an adverse event, the modified date and time will be constructed to match the first documented date/time post drug administration while preserving the order in which the AE was reported in the CRF.

[figure not shown]

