11.4. SERIOUS ADVERSE EVENTS AND UNEXPECTED ADVERSE EVENTS – DEFINITIONS

A Serious Adverse Event (SAE) includes (but is not limited to) an experience occurring at any dose that results in any of the following outcomes:

- Death
- A life-threatening event (i.e., the subject is at immediate risk of death from the reaction as it occurs). "Life-threatening" does not include an event that, had it occurred in a more serious form, might have caused death. For example, drug-induced hepatitis that resolved without evidence of hepatic failure would not be considered life-threatening even though drug-induced hepatitis can be fatal.
- In-patient hospitalization (hospital admission, not an emergency room visit) or prolongation of existing hospitalization.
- A persistent or significant disability/incapacity (i.e., a substantial disruption of the subject's ability to carry out normal life functions).
- A congenital anomaly/birth defect.

In addition, medical and scientific judgment should be exercised in deciding whether other situations should be considered an SAE (i.e., important medical events that may not be immediately life-threatening or result in death but may jeopardize the subject or may require medical or surgical intervention to prevent one of the other outcomes listed in the definition above). Examples of such medical events include (but are not limited to): allergic bronchospasm requiring intensive treatment in an emergency room or at home, blood dyscrasias or convulsions that do not result in in-patient hospitalization, or the development of drug dependency or drug abuse.

An **unexpected** AE is one for which the specificity or severity is not consistent with the current Investigator's Brochure. For example, hepatic necrosis would be unexpected (by virtue of greater severity) if the Investigator's Brochure listed only elevated hepatic enzymes or hepatitis.

Similarly, cerebral thromboembolism and cerebral vasculitis would be unexpected (by virtue of greater specificity) if the Investigator's Brochure listed only cerebral vascular accidents.

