# 9. Safety and Tolerability Analysis

All safety analyses will be performed on the safety analysis set.

Safety will be evaluated from reported AEs. No inferential statistical tests will be performed, unless otherwise specified.

For all safety and tolerability analyses, participants will be analyzed by the actual treatment.

All safety and tolerability data will be presented in listings.

[figure not shown]

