#### 9.1. Adverse Events

An AE is any undesirable event that occurs to a participant during a study, whether that event is considered related to Study Drug.

All summaries of AEs will be based on treatment-emergent adverse events (TEAEs) unless specified otherwise.

An adverse event is considered a TEAE if:

• The adverse event first occurred on or after the date of the first dose of study drug; or

• The adverse event was before the date of the first dose of study drug, but it increased in severity or became serious on or after the date of the first dose of study drug.

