#### 9.1.4. Summaries of Adverse Events

An overall summary of TEAEs will be provided by treatment. This summary will present number and percentage of participants with TEAEs per the following classifications:

- Participants with any TEAEs
- Participants with Treatment-Emergent Drug-Related AEs
- Participants with Treatment-Emergent AEs by Maximum Severity as Mild, Moderate, and Severe.
- Participants with TEAE leading to discontinuation from study
- Participants with Treatment-Emergent SAEs
- Participants with Treatment-Emergent SAEs leading to discontinuation from study
- Participants with Treatment-Emergent SAEs resulting in death

The following summary tables for TEAEs will be presented:

- Number and percent of participants reporting treatment-emergent AEs, grouped by MedDRA system organ class and preferred term
- Number and percent of participants reporting treatment-emergent drug-related AEs, grouped by MedDRA system organ class, and preferred term
- Number and percent of participants reporting treatment-emergent AEs, grouped by MedDRA system organ class, preferred term, and maximum severity
- Number and percent of participants reporting treatment-emergent SAEs will be tabulated by system organ class and preferred term and presented by treatment.
- Number and percent of participants reporting treatment-emergent AEs leading to study discontinuation, grouped by MedDRA system organ class and preferred term

For the summary tables above, the SOC terms and PTs will be presented in decreasing order of the total number of participants (frequency) who experienced each AE. System organ class terms and PTs with the same frequency will be presented alphabetically. In the case of multiple occurrences of the same TEAE within the same participant, each participant will only be counted once for each preferred term.

The following data listings for AEs will be provided for each participant by displaying the events captured on the CRF:

- All AEs,
- All serious AEs,
- All AEs leading to study discontinuation, and
- All AEs leading to Death.

In the AE data listings, all AEs will be displayed. AEs that are not treatment-emergent will be flagged in the AE listings.

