# 12.2. Safety Data

**Table 3: Safety Data** 

Table Number	Population Table Title / Summary				
14.3.1 Displays o	14.3.1 Displays of Adverse Events				
Table 14.3.1.1	Safety	Overall Summary of Treatment Emergent Adverse Events			
Table 14.3.1.2	Safety	Summary of Treatment Emergent Adverse Events by System Organ Class and Preferred Term			
Table 14.3.1.3	Safety	Summary of Treatment Emergent Drug-Related Adverse Events by System Organ Class and Preferred Term			
Table 14.3.1.4	Safety	Summary of Treatment Emergent Adverse Events by System Organ Class, Preferred Term, and Maximum Severity			
Table 14.3.1.5	Safety	Summary of Serious Treatment Emergent Adverse Events by System Organ Class and Preferred Term			
Table 14.3.1.6	Safety	Summary of Treatment Emergent Adverse Events Leading to Study Discontinuation by System Organ Class and Preferred Term			
14.3.2 Summary	14.3.2 Summary of Deaths, Other Serious and Significant Adverse Events				
Table 14.3.2.1	Safety	Listing of Serious Adverse Events			
Table 14.3.2.2	Safety	Listing of Adverse Events Leading to Study Discontinuation			
Table 14.3.2.3	Safety	Listing of Adverse Events Leading to Death			

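### SAP 6.1.6 and 9.1 disagree on when an adverse event carried over from the pivotal studies is treatment-emergent; under 6.1.6, one that turns serious at an unchanged grade drops out of the SAE counts

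*SAP*

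**What the plan says.** SAP 6.1.6, on data conventions, sets a rule for adverse events that were ongoing when the participant left PTI-125-06 or PTI-125-07: "Ongoing AEs from the pivotal studies will be classified as TEAEs in the current study only if they increase in severity", counted from the first dose in this study. The next sentence deals with the rest: "Otherwise, they will be classified as medical history events".

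SAP 9.1 defines a treatment-emergent adverse event (TEAE) for the whole analysis. An event with onset before first dose qualifies if "it increased in severity or became serious on or after the date of the first dose of study drug". Seriousness alone is therefore enough under 9.1.

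The summaries depend on that flag. SAP 9.1 bases AE summaries on TEAEs unless stated otherwise. The overall summary in SAP 9.1.4 has a row for "Participants with Treatment-Emergent SAEs", and Table 14.3.1.5 is the "Summary of Serious Treatment Emergent Adverse Events by System Organ Class and Preferred Term".

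**The concern.** Severity and seriousness are separate attributes. Severity (protocol 11.2, SAP 9.1.1) is a three-level grade of functional impairment. Seriousness (protocol 11.4, SAP 9.1.3) is defined by outcome. An event can meet a seriousness criterion without changing grade, and the two SAP sections then classify it differently.

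The likeliest route is a hospital admission. Protocol 11.4 lists "In-patient hospitalization (hospital admission, not an emergency room visit) or prolongation of existing hospitalization" as serious, and neither it nor SAP 9.1.3 exempts a planned admission for a stable condition. A rarer route is an event already graded Severe at entry. The scale has no higher grade, so under 6.1.6 it can never become treatment-emergent, whatever its later outcome. Exclusion 8 in protocol 5.3 bars moderate or severe ongoing events only when the investigator considers them a potential safety risk, so some can be present at entry.

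Adverse event incidence is the only endpoint in SAP 2.2.1, and SAP section 10 drops the laboratory, vital-sign, weight, ECG, examination, C-SSRS and HbA1c analyses. The same data could yield two different SAE tables, depending on which section is programmed.

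**Working it through.** The plan gives no figure to reproduce here; SAP 3.2 says no formal sample size was calculated. The check applies both rules to every combination of severity change and seriousness for an event ongoing at first dose.

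| Severity increased after first dose | Became serious after first dose | SAP 6.1.6 | SAP 9.1 |
|---|---|---|---|
| No | No | Medical history | Not a TEAE |
| Yes | No | TEAE | TEAE |
| Yes | Yes | TEAE and treatment-emergent SAE | TEAE and treatment-emergent SAE |
| No | Yes | Medical history, not counted | TEAE and treatment-emergent SAE |

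The rules agree in three rows and differ in the fourth. Every event that qualifies under 6.1.6 also qualifies under 9.1, so using 6.1.6 can only lower the counts.

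**Size.** The only input is the 1,081 participants in SAP 3.3, used as a proxy for the safety set, whose size is not stated.

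- One affected participant with no other treatment-emergent SAE: 100 × 1/1,081 = 0.0925, or 0.09 percentage points of overall SAE incidence.
- One affected participant who has another treatment-emergent SAE: 0, because the row counts participants.
- The number affected is not in the documents. Purely as illustration, 2, 5 or 10 such participants would give 100 × 2/1,081 = 0.19, 100 × 5/1,081 = 0.46 or 100 × 10/1,081 = 0.93 points.

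**In the SAE table by preferred term.** SAP 4.1 says: "Percentages will be presented to 1 decimal place, unless otherwise specified". A serious preferred term reported by that participant alone reads 1 (0.1%) under 9.1. Under 6.1.6 the table has no row for it.

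**Listings.** SAP 9 says: "All safety and tolerability data will be presented in listings", and SAP 9.1.4 promises listings of all AEs and all serious AEs, with events that are not treatment-emergent flagged. The event should appear there if it stays in the AE data. That is not certain once it has been reclassified: SAP section 12 plans no medical-history listing, and the subject-level listing 16.2.7.1 is titled for treatment-emergent events. In any case, a listing does not correct an incidence table.

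**The case against.** The strongest reply is that 6.1.6 is a specific rule for carried-over events and 9.1 a general one, so both can stand. Protocol 7.1.1 and SAP 6.1.1 allow the End-of-Treatment visit and Study Day 1 to fall on different dates. An event starting in that gap would come under 9.1 without clearly being ongoing from a pivotal study. This does not remove the conflict. Section 6.1.6 does not call itself an exception, and 9.1 does not refer to it. Protocol 11.1 starts AE monitoring at dosing, so nearly all events with earlier onset come from the pivotal studies. The seriousness clause in 9.1 would have almost nothing to act on.

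The other points are fair and limit the size:

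- Section 9.1 is the formal definition and sits just above the table specifications, so a programmer may well follow it. The omission arises only if 6.1.6 is used instead.
- A mild or moderate event with a fatal, life-threatening or disabling course would normally be regraded under protocol 11.2. So would many unplanned admissions. Both rules then count it. Much of what remains is planned admission for stable conditions, which says little about drug safety.
- A site may record the change as a new adverse event, as protocol 11.1 permits for exacerbations. Both rules count that too.
- There may be no affected events at all.

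**Conclusion.** The concern holds, as a minor internal inconsistency. The difference in wording is certain, and no text sets precedence. The effect on reported SAE incidence is not known: at most 0.09 percentage points per affected participant, downward only, and possibly zero overall. This rests on three assumptions: that 1,081 approximates the safety set, that 6.1.6 rather than 9.1 is programmed, and that the site kept the event as one continuing record at an unchanged grade. The study is single-arm, SAP 4.1 calls it exploratory, and no test or threshold depends on the count. It is still worth settling, because treatment-emergent AE counts are the core of what will be reported.

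**What to change.** Keep a single TEAE definition, in SAP 9.1. In 6.1.6, either extend the condition so that a carried-over event also qualifies when it becomes serious from the first dose in this study onward, or replace the sentence with a reference to 9.1.

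If outputs already exist, state which rule produced them and check the data for carried-over events that became serious at an unchanged grade. If there are none, the two rules give identical tables and a note to that effect is enough. If there are any and 6.1.6 was used, rerun Tables 14.3.1.1 to 14.3.1.6 under 9.1.

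The cost is one clause in the SAP and, at most, a rerun of six tables. Reported SAE incidence may become slightly less favourable.

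### SAP 6.1.6 gives two rules for partial AE onset dates and no precedence; for some AEs known to have stopped before first dose, only one rule makes them treatment-emergent

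*SAP*

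**What the plan says.** Both rules stand in SAP 6.1.6. Call them A and B.

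- **Rule A** (the paragraph on partial AE start dates) uses the end date. If the recorded part of the onset matches first dose and "the end date is on or after the first dose date, or AE is ongoing, then the date is assigned the first dose date". When only the day is missing, "if the month and/or year do not match the first dose date or the end date is prior to the first dose date" sends the onset to the first of the recorded month. When the month, or day and month, is missing, a year mismatch or an end date before first dose sends it to 1 January of the recorded year.
- **Rule B** (the later paragraph on partial dates) never mentions the end date. Day missing: "the day assigned is the first day of the month or the date of first dose (if in the same month), whichever is later". Month missing: the first-dose month is used, "unless that results in a date before the first dose in which case the month after the first dose is used". Day and month missing: the first-dose month, on the later of its first day and the first-dose date.

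Rule B is not a fallback for other kinds of date: "These conventions will be applied only to adverse event onset dates and times". It adds a precaution that aligns an imputed AE onset with the first documented time after dosing.

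Three related provisions matter. For partial end dates, "if only the day is missing, then the day is assigned the last day of the month", and if the month is missing too, 31 December is used. AEs continuing from the phase 3 studies have their own rule: "Ongoing AEs from the pivotal studies will be classified as TEAEs in the current study only if they increase in severity". SAP 9.1 counts an AE as treatment-emergent (TEAE) if it first occurred on or after the first-dose date, or worsened or became serious from then on.

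SAP 6.1.4 sends the reader to section 6.1.8 for incomplete AE dates, but section 6.1 ends at 6.1.6.

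**The concern.** Two programmers could each follow SAP 6.1.6 faithfully and classify the same AE differently. One of the two results would also be impossible on its face: an AE that begins after it has ended.

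Classification matters more here than in most extension studies. SAP 9 evaluates safety from reported AEs, and SAP 9.1 bases the AE summaries on TEAEs unless otherwise specified. SAP 10 drops the laboratory, vital-sign, weight, examination, ECG, C-SSRS and HbA1c summaries because the study ended early. The date rule therefore decides which partially dated events enter nearly all the safety evidence that remains.

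**Working it through.** The plan gives no figure to reproduce. The check applies both rules to the same records and then the SAP 9.1 onset test (imputed onset on or after first dose).

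**Readings used.** Rule A's condition is taken as (end date on or after first dose, or AE ongoing). Rule B keeps the recorded year. Rule B's precaution is set aside at this stage.

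**Worked examples, assumed first dose 20-Mar-2023**

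| Recorded onset | Stop date | Rule A | Rule B | Rule B onset minus stop |
|---|---|---|---|---|
| Mar-2023, day missing | 10-Mar-2023 | 01-Mar, not TEAE | 20-Mar, TEAE | 20 − 10 = 10 days |
| 2023 only | 10-Feb-2023 | 01-Jan, not TEAE | 20-Mar, TEAE | 18 + 20 = 38 days |
| Day 05, month missing, 2023 | 10-Feb-2023 | 01-Jan, not TEAE | 05-Apr, TEAE | 18 + 31 + 5 = 54 days |

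In the third row Rule B first forms 05-Mar, which precedes first dose, and so moves to April. The worsening limb of SAP 9.1 cannot apply, because these AEs had ended before dosing.

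**Every first-dose date in 2023 paired with every earlier stop date in 2023**

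- Year only known: 365 × 364 / 2 = 66,430 pairs. The rules disagree in all of them.
- Day missing, stop in the first-dose month: 7 × 465 + 4 × 435 + 378 = 5,373 pairs. The rules disagree in all of them.
- Month missing, recorded day 1, 10 or 28: 3 × 66,430 = 199,290 combinations. If Rule B may roll a December first dose into the next year, the rules disagree in all. If the recorded year is kept, they agree in 10,485 + 7,434 + 1,089 = 19,008 combinations (recorded days 1, 10 and 28 respectively) and disagree in 199,290 − 19,008 = 180,282.

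These counts show that the conflict is systematic within the defined pattern. They say nothing about how often the pattern occurs.

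**Where the rules do not conflict**

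- December: first dose 20-Dec-2023, onset day 05 of an unknown month in 2023, stop 10-Dec-2023. Rule A gives 01-Jan-2023. Rule B, with the year kept, gives 05-Jan-2023. Neither is a TEAE.
- Stop day also missing in the first-dose month: in the first row of the table, Rule A imputes the stop to 31-Mar, so both rules give 20-Mar, TEAE.
- Day missing in an earlier month of the same year: onset Feb-2023, stop 28-Feb-2023. Both rules give 01-Feb, not TEAE.

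**Precaution read literally.** It moves imputed onsets to after dosing without checking the end date. The last example then becomes 01-Feb (not TEAE) under A and 20-Mar under B: a TEAE that starts 20 days after it ended. The clause widens the conflict.

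**Size per record.** SAP 3.3 gives 1081 participants. One participant wrongly counted changes a row by 1/1081 = 0.0925%, about 0.09 percentage points.

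**The case against.** The best reply is that few, if any, records will be affected. An AE must have a partial onset date, a stop date known well enough to precede first dose, a matching first-dose month or year, and an entry in this study's data although it resolved before dosing. Protocol 11.1 starts AE monitoring at dosing, and AEs continuing from phase 3 have their own rule. This largely stands. It does not show that the set is empty: Rule A has a branch for AEs that ended before first dose, AEs are scheduled for collection on Study Day 1, and SAP 9.1.4 flags AEs that are not treatment-emergent.

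A second reply is that extra TEAEs are the cautious error, in line with imputing missing severity as severe and missing relationship as related. But an onset after the AE's own stop date is an invalid record, not a cautious one. Nor is the direction the same under every reading. With first dose 20-Dec-2023, onset day 05 of an unknown month in 2023 and stop 28-Dec-2023, Rule A gives 20-Dec (TEAE), while Rule B with the year kept gives 05-Jan-2023 (not TEAE).

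A third reply is that Rule A is the more specific and would naturally prevail. The SAP does not say so, and Rule B expressly confines itself to AE onset.

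A reader might infer that any AE that ended before first dose, with onset somewhere in the first-dose year, is classified differently. The documents do not support that: as the February example shows, the year match matters only when the month is missing.

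**Conclusion.** The inconsistency is real and narrow. It concerns AEs with a stop date known to precede first dose whose onset either lacks only the day and matches the first-dose month and year, or lacks the month and matches the first-dose year. For these, Rule A gives a pre-dose onset and Rule B a post-dose onset later than the stop date, subject to the December and incomplete-stop-date exceptions.

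That result rests on the three readings stated in the working. That two rules overlap with no stated precedence does not depend on them.

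A reader might also infer that the TEAE tables are materially inflated or a comparison biased. Neither follows. The number of affected AEs cannot be derived from the documents, the effect is about 0.09 percentage points for each participant wrongly counted, and SAP 3.5 gives everyone the same treatment, so no between-group comparison is affected. It is a minor correction, worth making because so little other safety analysis remains.

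**What to change.** In SAP 6.1.6:

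1. State that Rule A governs partial AE onset dates, and bracket its condition as (end date on or after first dose, or AE ongoing).
2. Delete Rule B's date paragraph, and the post-dosing precaution as it applies to dates.
3. Keep the partial-time rules.

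In SAP 6.1.4, change the reference from 6.1.8 to 6.1.6.

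Rule A already covers every partial-date case in Rule B, so nothing is left without a rule. There is one small loss: when only the month is missing, Rule A discards the recorded day. For first dose 20-Mar-2023 and an ongoing AE recorded as day 25 of an unknown month in 2023, Rule A assigns 20-Mar, whereas Rule B keeps the 25th. Both are TEAEs.

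The treatment of AEs with no start date at all ("Adverse events with entirely missing start dates will be classified as treatment-emergent, as appropriate") is a separate matter and need not be reopened here.

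The cost is a version-controlled amendment to the finalized SAP 1.0: edits to the AE date text in 6.1.6 and one cross-reference, with no new data or outputs.
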